	Appendix 2 – Head and Neck MD Anderson Symptom Inventory (MDASI-HN)	48
	Appendix 3 – Xerostomia Questionnaire.....	50
	Appendix 4 – Penetration/Aspiration Scale.....	52
	Appendix 5 – Montreal Cognitive Assessment	53
	Appendix 6 – MD Anderson Dysphagia Inventory (MDADI).....	54

SCHEMA

Treatment Plan:

The protocol combines *selective* RT dose de-escalation (from 70 Gy to 63 Gy and from 58.1 Gy to 50.75 Gy, same number of fractions (N=35) in 7 weeks) in patients with HPV-associated cancers of the oropharynx receiving standard of care treatment based on clinical stage. Image guided RT with daily cone-beam CT imaging will be used with CTV to PTV margins of 5 mm. Outcome will be evaluated both in terms of tumor control (and pattern of failure) and toxicity/QoL. Endpoints: Prevalence of grade 3+ toxicity at 2 yrs according to CTCAE 4.0 <15%; locoregional control at 2 yrs >85%.

SCC oropharynx, HPV positive,

Tx, T1-2 and Nx (without ECE), N0-1, N2a (<5 cm) → de-escalated IMRT alone ± S for residual disease

T3 and/or Nx (with ECE) N2a (≥5 cm), N2b-c, N3 (resectable) → de-escalated IMRT + conc CDDP ± S for residual disease

Eligibility:

- Confirmed histopathologic diagnosis of oropharyngeal (*tonsil, base of tongue, pharyngeal wall, soft palate*) squamous cell carcinoma;
- Human papillomavirus (HPV) positive;
- Stage T1-T3, N0-N3 (resectable), M0; both sides of the neck are judged to be at risk of metastatic disease
- Surgery of the primary tumor is limited to incisional or excisional biopsies; any surgery is allowed in the neck; patients with surgery at both primary and nodal sites and without macroscopic residual disease (cTxcNx) are excluded)
- ANC \geq 1200 /mm³
- Platelets >100,000/ mm³
- Adequate hepatic function with bilirubin < 1.5 mg/dl
- AST < 2x the upper limit of normal
- ALT < 2x the upper limit of normal
- Serum creatinine < 1.3 mg/dl
- Normal serum calcium (or normal corrected serum calcium)
(Please note*: Formula for corrected calcium if albumin value is below normal range: Corrected calcium (mg/dl) = [4 – [patient albumin (g/dl)] x 0.8 + patient calcium (mg/dl)
- Cannot have Serum creatinine >1.3 or ULN
- Cannot have CCL < 60 cc/min
- ECOG performance status 0-1
- Nutritional condition must be considered compatible with the proposed radiotherapeutic treatment (cannot have unintentional and/or surgically unrelated weight loss >20% in the preceding 3 months)
- Patients cannot be a current smoker at time of treatment

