1.5 Strategies to decrease toxicity

There are several steps that can potentially reduce or mitigate the risk of toxicity. Regarding IMRT, there are several levels of intervention as illustrated in table 2.

Table 2. Examples of radiation treatment de-intensification strategies

Strategy	Feature	Example
Dose reduction	To high dose volume	Lower Px dose (S1)
	To low dose volume	Lower Px dose (S3)
	To organs at risk	To PTV-OAR overlap (S2) SF-IMRT Surgical transfer of submandib gland Avoid medial RP nodes
Volume reduction	Contoured CTV3	Avoid anterior part of ipsi lv IB
	CTV3	Avoid controlat lvs IB & V
	CTV3	Allow unilateral tmt only
	CTV3	Reduce volume
	CTV2	Limit to metabolically active
	CTV1	

Irradiated

Reduce CTV to PTV exp – IGRT
Brachytherapy boost

Dashed: strategies exploited in the current protocol

We have identified a solution that involves several individual strategies, as extensively discussed elsewhere³⁸. Briefly, in the context of dose painting IMRT (where CTV1 covers the gross tumor volume, CTV3 the volume at low (<10%) risk of microscopic disease, and PTV1-3 represent an expansion of CTV1-3 to account for set-up errors and tissue deformation), we plan a reduction of the prescription dose from 70 Gy equivalent dose at 2 Gy per fraction (ED2) for PTV1 and from 50 Gy ED2 for PTV3 to 60 Gy ED2 and 44 Gy ED2, respectively. The rationale of the entity in dose reduction is reported in table 3. How these `experimental` doses compare to standard ones is reported in table 4.

Table 3. Radiobiologic considerations on dose de-escalation

	Subclinical disease	Gross disease
General assumptions and definitions	
 10 fold reduction of cell population means 1 Log or elimination of 90% of cells; D_{10} is defined as the dose necessary to depopulate by 1 Log; $D_{10}=D_0 \times 2.3$; Typical value of D_0 is 1.5-2.5 Gy (3 Gy if only hypoxic cells were present); here we consider 2.5 Gy; According to Poisson statistics, 90% of local control means that the average number of cells surviving is about 0.1 or 10^{-1}; 99% means 0.01 or 10^{-2}; If a tumor is composed by 10^{10} cells to begin with, in order to achieve a LC of 90%, 10^{11} cells need to be killed (from 10 to -1 Logs, thus 11) 	

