Specific assumptions	
 In `high` risk areas at containing microscopic disease, tumor population is 10^7 cells; To achieve 90% of local control, 8 Logs of cells need to be killed; 	
 Subtotal resection, leaving 1% or 0.01 of cells, depopulates by 2 Logs;
Estimates	
If each Log is depopulated with 5.75 Gy (2.5 Gy x 2.3), then:
 
→ 8 Logs would need 46 Gy (5.75 Gy x 8);
 
→ 9 Logs, 51.75 Gy
	
→ 12 Logs would require 69 Gy
 
→ 11 Logs, 63.25 Gy
 
→ 10 Logs, 57.5 Gy

Comments	These estimates would be consistent with the standard dose of 50 Gy for regions treated electively or at `low` risk;	Consistently, after tonsillectomy with 10^{8-9} Logs left, the Px dose is between 60 Gy and 66 Gy;
Role of concomitant chemotherapy	
Concomitant chemotherapy equals to a biological equivalent dose (BED) of ≈ 10 Gy³⁹;
 
→ in presence of chemotherapy, a $BED_{10} \approx 10$ Gy lower than needed would be expected from RT;
	

Estimates	a BED ₁₀ of 8-12 Gy corresponds to 8-10 Gy or 1-2 Logs; In presence of concomitant chemotherapy, the dose of RT for microscopic disease would drop to ≈40 Gy for areas at low risk and to ≈50 Gy for areas at high risk	The dose of radiation would drop to ≈60 Gy
Comments on disease control	44 Gy at 2 Gy per fraction is allowed by NCCN guidelines to treat electively the neck in presence of chemotherapy ⁴⁰	Clinical data obtained combining `reduced dose RT` and concomitant chemotherapy seems to be consistent to these estimates ⁴¹ .
Comments on toxicity	Structures that are expected to benefit from less than 70 Gy (due to their proximity to the target), include the mandible, the constrictor mm, the larynx, the brachial plexus; Structures that benefit from an intermediate dose level reduction include the parotids, the submandibular glands, great vessels in the neck, masticatory mm, thyroid gland, esophagus	

Table 4. Equivalency of schedules in terms of radiobiological parameters

	Treatment parameters				ACUTE TOXICITY TUMOR RESPONSE		LATE TOXICITY	
	D (Gy)	d (Gy)	# fxs	OTT (dd)	BED ₁₀ [†] (Gy)	LQED ₂ [†] (Gy)	BED ₃ [*] (Gy)	LQED ₃ [*] (Gy)
Micro low risk (CTV3)								
Standard 3FT	50	2	25	33	55.2	50	83.3	50
IMRT	58.1	1.66	35	47	57.4	≈52	90.2	≈54
Experimental	50.75	1.45	35	47	47.8	≈42 (-16%) [^]	75.3	≈45 (-10%) [^]
Micro high risk (CTV2)								
Standard 3FT	60	2	30	40	64.5	60	100	60
IMRT	63	1.8	35	47	64	≈60	100.8	≈60
Macro-GTV (CTV1)								

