5.5 PTV and subPTV generation

Each CTV is expanded 5 mm isotropically to generate corresponding PTV's, PTV1, 2 and 3. Each PTV is further adjusted to come off the skin, by excluding the part that is within 3 mm to skin surface (PTV= CTV + 5mm – (skin -3mm)).

In order to achieve dose de-escalation on parts of the PTV (subPTV), each PTV is further divided into subPTV's whose prescription dose is as follows in table 6.

Table 6

Main PTV	SubPTV	Note	Px D (Gy)	Nomenclature
PTV1	overPTV1	Part of PTV1 that overlaps with larynx for edema+8 mm, superior constrictor m+8 mm, mandible + 8 mm, parotids, masticatory mm, esophagus, mid/low constrictor mm	63	PTV63
	truePTV1	Rest of PTV1	70	PTV70
PTV2	None		63	PTV63
PTV3	overPTV3	Part of PTV3 that overlaps with larynx for edema+8 mm, sup/mid/low constrictor mm+8 mm, parotids+8 mm, masticatory mm+8 mm, esophagus+8 mm	50.75	PTV50.75
	lowPTV3	Part of PTV3 that covers ipsilateral (to neck disease if present) level IV (and level III is negative) and/or contralateral (to neck disease or both heminecks if no neck disease is present) levels III and IV; if disease is present on both sides, each side is treated as ipsilateral one	50.75	PTV50.75
	truePTV3	Rest of PTV3 (or without lowPTV3 and overPTV3)	58.1	PTV58.1

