10 STATISTICAL CONSIDERATIONS

10.1 Sample Size

The accrual rate for this study is expected to be approximately 10 patients per year, over a 6-year accrual period. This would yield an expected sample size of 60 patients. The primary objective of this study is to estimate the prevalence of toxicity and efficacy two years following treatment administration. We expect approximately 15% of patients to die before reaching two years post-treatment, so our sample size for evaluation of our primary objective has been adjusted to 50 patients. The goal of this study is to demonstrate a maximum grade 3+ toxicity rate of 15% between six months and two years after treatment administration and a minimum locoregional tumor control rate (efficacy) of 85%. The table below shows the precision we have to estimate these endpoints with a sample size of 50 patients.

Endpoint	Prevalence	Exact 95% Confidence Interval	Precision (Half the width of the confidence interval)
Toxicity	2%	0.05 – 11%	5.5%
	6%	1 – 17%	8%
	10%	3 – 22%	9.5%
	14%	6 – 27%	10.5%
Efficacy	84%	71 – 93%	11%
	90%	78 – 97%	9.5%
	94%	83 – 99%	8%

The locoregional tumor control rate in this patient population is expected to be at least 85%. We will ensure that this treatment does not reduce toxicity at the expense of efficacy. At the same time, we will monitor for excess toxicity. If convincing evidence develops that:

- Locoregional control failure rate exceeds 25%; or
- Prevalence of new grade 3+ toxicities six months post-treatment exceeds 25%, the study will stop pending a data safety monitoring committee review. The complete stopping

guideline scenarios are shown in the table below, with the proportion of toxicities and failures being considered for the first 10, 20, 30 and 40 patients enrolled. For example, if 9 of the first 20 patients have a grade 3+ toxicity six months after treatment, the study will stop. If 9 patients have either a grade 3+ toxicity or fail, e.g., 4 have toxicity and 5 fail, the trial will not stop. Once the 40th patient reaches six months of follow-up, we expect to have enrolled 48 out of the total 60 patients on the study. At this point, monitoring for excess toxicity or failures will stop, as the trial's accrual phase will nearly be completed. The upper bound for the confidence intervals is 100%.

Toxicity [Locoregional Control Failure Rate]	Number of patients who develop a toxicity [fail]	Number of patients enrolled	Lower bound of exact one-sided 90% confidence interval

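### The size of the dose reduction is argued with concurrent chemotherapy but also applied to IMRT-alone patients, and pooled monitoring could miss excess locoregional failure confined to them

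*Combined protocol and SAP*

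**What the plan says.** **Rationale.** Section 1.5 plans a reduction "to 60 Gy ED2 and 44 Gy ED2, respectively" for PTV1 and PTV3, and adds: "The rationale of the entity in dose reduction is reported in table 3". In Table 3 the relevant block opens with "Concomitant chemotherapy equals to a biological equivalent dose (BED) of" about 10 Gy. From that credit it derives about 60 Gy for gross disease. For microscopic disease it says "In presence of concomitant chemotherapy, the dose of RT for microscopic disease would drop to" about 40 Gy in low-risk areas and about 50 Gy in high-risk areas. Both comments on disease control concern radiotherapy given with chemotherapy. One is "44 Gy at 2 Gy per fraction is allowed by NCCN guidelines to treat electively the neck in presence of chemotherapy"; the other cites clinical data on reduced-dose radiotherapy combined with chemotherapy.

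**Who receives it.** The Schema has two regimens. Patients with Tx or T1-2 disease and N0-1, N2a below 5 cm, or Nx without extracapsular extension get "de-escalated IMRT alone ± S for residual disease". Those with T3 and/or more advanced nodal disease get the de-escalated IMRT with cisplatin. In section 5.5 "each PTV is further divided into subPTV's whose prescription dose is as follows in table 6"; Table 6 lists 63 Gy (overPTV1) and 50.75 Gy (overPTV3, lowPTV3) with no condition on chemotherapy.

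**Monitoring and reporting.** Section 10.1 says "The locoregional tumor control rate in this patient population is expected to be at least 85" per cent. It counts failures in the first 10, 20, 30 and 40 patients together, with boundaries of 5, 9, 12 and 15. Section 10.3.1 reports locoregional control for all patients. Neither section separates the regimens.

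**The concern.** The argument for how far the dose can come down uses a contribution from chemotherapy that one of the two regimens does not receive. If the assumption behind treating both alike is wrong, the excess failures would arise in the IMRT-alone patients. The stopping rule and the primary efficacy estimate both mix these patients with chemoradiation patients, so the trial could run to completion, and even report control at its 85% objective, with poor control in one regimen. At stake is whether the plan's locoregional safeguard can detect a problem in the patients for whom it offers no explicit derivation of the reduction.

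**Working it through.** **1. The plan's own figures.** The one-sided 90% Clopper-Pearson lower bound is the 10% quantile of Beta(r, n − r + 1). For 5/10, 9/20, 12/30 and 15/40 it gives 26.7%, 29.3%, 27.7% and 27.1%, as in 10.1.

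Table 4 uses BED10 = D(1 + d/10) − ln 2 × (OTT − 21)/(0.35 × 5). For 47 days the time term is 0.693 × 26/1.75 = 10.30 Gy.
- 70 Gy: 84.00 − 10.30 = 73.7
- 63 Gy: 74.34 − 10.30 = 64.0
- 58.1 Gy: 67.74 − 10.30 = 57.4
- 50.75 Gy: 58.11 − 10.30 = 47.8

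All match Table 4.

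**2. Reduction against the chemotherapy credit.** Relative to standard IMRT, BED10 falls by 73.7 − 64.0 = 9.7 Gy in the reduced part of PTV1 and by 57.4 − 47.8 = 9.6 Gy in the reduced part of PTV3. Each is nearly the whole 10 Gy that Table 3 credits to chemotherapy.

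**3. What the pooled rule can detect.** Assumptions, since the documents give neither figure: the IMRT-alone share w is 50%, 30% or 20%; true failure is 35% with IMRT alone and 10% with chemoradiation. Failure status is taken as known at each look. Pooled failure is 0.35w + 0.10(1 − w). The probability of crossing any of the four boundaries comes from sequential binomial calculation.

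| IMRT-alone share | Pooled failure | Pause, pooled rule | Pause, pooled plus IMRT-alone count |
|---|---|---|---|
| 50% | 22.5% | 8% | 35% |
| 30% | 17.5% | 2% | 24% |
| 20% | 15.0% | 1% | 11% |

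With 40% failure in IMRT-alone patients the pooled rule still pauses only 13.3%, 3.4% and 1.5% of the time.

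The 40-patient look shows why. At a 30% share there are 12 IMRT-alone and 28 chemoradiation patients. The latter contribute 28 × 10% = 2.8 expected failures, so 15 − 2.8 = 12.2 IMRT-alone failures would be needed, more than the 12 patients available. At a 20% share, pooled control is 100 − 15 = 85%, exactly the objective, despite 35% failure in one regimen.

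**4. The added count.** Within IMRT-alone patients, the smallest counts whose one-sided 90% lower bound exceeds 25% are:
- 4 of 5 (41.6%; 3 of 5 gives 24.7%)
- 5 of 10 (26.7%)
- 7 of 15 (28.2%; 6 of 15 gives 22.6%)
- 9 of 20 (29.3%; 8 of 20 gives 24.9%)

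Simulating 400,000 trials of 40 patients, pausing on either rule, gives the last column above. The same simulation with 15% failure in both regimens gives pause probabilities of 2.1%, 1.9% and 1.5% at shares of 50%, 30% and 20%, against 1.1% for the pooled rule alone.

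**The case against.** A reader might infer from Table 3's log-kill model that IMRT-alone patients will lose control. The documents do not support this, for four reasons.

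- **Elective neck.** Control = exp(−N × 10^(−D/5.75)) gives 61% at 42 Gy for N = 10^7 cells, but Table 3 assigns 10^7 to high-risk areas, which stay at 63 Gy as PTV2. At 10^6 cells the same formula gives 95%. Section 5.3.1 also puts the risk of involvement in CTV3 at only 5-15%.
- **Gross disease.** With 15% of PTV1 reduced from 70 to 60 Gy and 10^10 cells spread evenly, the formula gives 94.1% against 99.3% at full dose. However, 10^10 is Table 3's general example, and IMRT-alone patients are the lower-stage group. At 10^9 cells it gives 99.4%. Section 1.5 says more than 85% of each PTV keeps standard dose, and overPTV1 may be largely margin.
- **Rationale.** It would also be too strong to say the reduction has no basis without chemotherapy. Table 3 has rows without it (10 logs 57.5 Gy, 11 logs 63.25 Gy), and section 1.2 describes early T stage and HPV-positive disease as favourable. These may justify the design, but the plan does not offer them as the derivation for IMRT-alone patients.
- **Failure rates.** The 35% scenario is assumed to probe the rule; neither the documents nor the model predict it.

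These points stand, and they limit the concern to an unstated assumption. They do not answer the monitoring point, which does not depend on the model. It is also fair to say that a rule within one regimen of a 60-patient study has modest power. At a 20% share, fewer than a third of trials would reach even 10 IMRT-alone patients among the first 40.

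**Conclusion.** The concern holds in limited form. Table 3's stated drops and both of its disease-control comments presuppose chemotherapy, the same reduced levels apply without it, and no section gives the reasoning for IMRT-alone patients or looks at them separately. This is a gap in justification and in monitoring sensitivity, not a finding that the treatment is inadequate. Its size, under the assumed 35% and 10% failure rates and shares of 20% to 50%, is a 1% to 8% chance that the pooled rule pauses the trial, against 11% to 35% with the added count. True sensitivity would be lower under either rule: monitoring ends when patient 40 reaches six months, so later failures are not counted.

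The elective-neck dose is 44 Gy ED2 in the section 1.5 text but about 42 Gy in Table 4. That is a separate mismatch to reconcile and carries no weight in the monitoring argument.

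**What to change.** 1. **Section 10.1.** Keep the pooled count. In addition, apply the same criterion (exact one-sided 90% lower bound above 25%) to locoregional failures among IMRT-alone patients alone, at looks that group can reach, for example 4/5, 5/10, 7/15 and 9/20. Crossing would trigger the same pause for committee review.
2. **Section 10.3.1.** Report locoregional control with its exact 95% interval by regimen as well as overall. This would be descriptive: of 50 evaluable patients a 20% share is 10 and a 50% share is 25, and failure of 2/10 or 4/25 has an interval of 2.5-55.6% or 4.5-36.1%.
3. **Section 1.5.** The sponsor should reconcile Table 3 with the Schema and Table 6 by stating the expected control in IMRT-alone patients and its basis without the chemotherapy credit, and should reconcile 44 Gy with about 42 Gy. Which dose applies is the sponsor's decision.

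The cost is a short amendment using data already collected, with no extra patients and about 1 percentage point or less of additional unnecessary pauses when failure is 15% in both regimens.

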1.6 Standard Supportive treatment

Regarding supportive treatment and prophylactic measures to prevent/mitigate toxicity, the following ones are generally pursued as standard of care:

- Dental evaluation and fluoride prescription/administration;
- Speech pathology evaluation including
- Baseline swallowing screening with flexible endoscopic evaluation of swallowing (FEES) followed by a formal modified barium swallowing study (MBSS) if needed. The Penetration/Aspiration Scale (Appendix 4) will be used during modified barium swallow studies.
 - + baseline evaluation of jaw opening, premorbid speech disturbance and dysphonia.
 - + baseline cognitive/language function screening using the Montreal Cognitive Assessment (Appendix 5).
 - + implementation of prophylactic swallowing and trismus prevention exercises prior to initiation of treatment⁴⁶;
 - + education regarding the role of oral hygiene and aspiration pneumonia, products to compensate for xerostomia (e.g., frequent sips of water, oral lubricants, saliva substitutes) and dentrifices.
 - + documentation of the presence of a gastrostomy feeding tube, estimated percent of oral alimentation/hydration via the feeding tube; estimated percentage of PO intake at baseline.
- Nutritional evaluation with pre-treatment correction of weight loss (nutritional impairment is defined as weight loss > 20% in the preceding 3 months or food

intake below 50% of normal requirements in the week preceding enrollment) as needed. A PEG-tube will be placed routinely before or shortly after initiation of IMRT only in those patients who receive chemotherapy in addition to radiotherapy.

2 OBJECTIVES

2.1 To achieve a prevalence of grade 3+ late toxicity at 2 yrs <15% while maintaining a locoregional tumor control >85±7% at the same time interval (toxicity is scored at 5.11 and 9.5 and locoregional control at 9.4);

2.2 To determine the nature and prevalence of side effects at different time intervals and describe their relationship to pretreatment function and local dose and treated volume.

2.3 To determine the quality of life of surviving patients (5.11 and 9.5)

3 SELECTION CRITERIA

3.1 Eligibility Criteria

3.1.1 Biopsy-proven SCC of the oropharynx (*tonsil, base of tongue, pharyngeal wall or palate*),

3.1.2 Tumor positive for infection with human papillomavirus (HPV) virus (any subtype) as per JH Pathology assessment (section 8.0);

3.1.3 Negative pregnancy test for women of childbearing potential

3.1.4 T stage: 1, 2, 3. Surgery of the primary tumor is limited to incisional or excisional biopsies (i.e. tonsillectomy) even without macroscopic disease left. Positive resection margins and/or gross residual disease at the *primary* site are allowed; evaluation of primary tumor extent may require the use of a flexible fibroscope if deemed clinically necessary by the treating physician; any N stage but resectable; lymph nodes in both sides of the neck are at risk of metastatic disease, according to clinical judgment, and require irradiation; pre-treatment surgery in the neck in the forms of incisional/excisional biopsy or a multilevel neck dissection is allowed only if there is gross tumor left at the primary site;

3.1.5 No other malignancy except for non-melanomatous skin cancer, early stage prostate cancer (T<2a and PSA<10 and GLS<7) or a carcinoma not of head and neck origin disease free for > 5 yrs.

3.1.6 - ANC > or = to 1000 /mm³

- Platelets >100,000/ mm³

- Adequate hepatic function with bilirubin < 1.5 mg/dl

- AST < 2x the upper limit of normal

- ALT < 2x the upper limit of normal

- estimated CCL ≥ 60 cc/min

- Normal serum calcium (or normal corrected serum calcium) (Please note*:

Formula for corrected calcium if albumin value is below normal range: Corrected calcium (mg/dl) = [4 – [patient albumin (g/dl)] x 0.8 + patient calcium (mg/dl)

- 3.1.7 Cannot have distant metastasis (M0);
- 3.1.8 ECOG performance status 0-1
- 3.1.9 Patient's nutritional and general physical condition must be considered compatible with the proposed radiotherapeutic treatment (cannot have unintentional and/or surgically unrelated weight loss > 20% in the preceding 3 months). *This assessment is a standard of care assessment for this patient population. This requirement can be waived by the investigator if the subject has an identifiable procedure which is the immediate and sole cause for the weight loss without an underlying pathological cause. An example of a situation like this would be if a participant is found to need a tonsillectomy during the pretreatment evaluations. It's obvious that this scenario would be a non-pathological reason for such a weight loss. The PI will only have this ability to waive this criterion if and only if he can substantiate and document that the weight loss does not have a pathological etiology and will correct itself within a reasonable and acceptable period of time
- 3.1.10 Patient is judged to be mentally reliable to follow instructions and to keep appointments. (Please note that mental reliability is not determined through any specific test rather it is ascertained by the treating physician through conversation at the time of consult)
- 3.1.11 No concurrent enrollment in another therapeutic protocol for the same diagnosis;
- 3.1.12 Signed study-specific informed consent prior to registration.
- 3.1.13 Subject must understand that while they are on study they cannot have any concurrent curative therapy for their cancer other than what is outlined in the protocol.

